5. STUDY OBJECTIVES

The primary aim of this feasibility study is to evaluate the preliminary safety and performance of the PEPNS System in patients that need to be mechanically ventilated in the Intensive Care Unit (ICU). Specific objectives are as follows:

- (a) Determine whether pacing the diaphragm would be of benefit to the difficult to wean patient cohort in the ICU.
- (b) Examine whether the placement of the phrenic nerve pacing leads between the anterior scalene and sternocleidomastoid muscles in the patients' neck would cause significant other muscular contraction (arm movements – brachial plexus transmission,) or local contractions (the muscles of the neck themselves - Sternocleidomastoid, Anterior scalene muscles).
- (c) Determine stimulation levels necessary to elicit a change in the Work Of Breathing measurement as determined by the wye pneumotachograph and pressure sensor.
- (d) Determine whether pacing the diaphragm will result in a progressive increase in tidal volume (or volume per breath) within the 48-hour period of the study.
- (e) Determine if diaphragm thickness can be characterized over the 48 hours of electrical stimulation, if feasible.

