11.2 Index Procedure

Once the study subject or authorized representative signs an ICF and his/her eligibility to participate in the study is confirmed, the PEPNS System procedure can be initiated. A primary operator will be performing the PEPNS System procedure, but an additional qualified operator may be present or assisting. A Stimdia representative may also be present during index procedure to provide technical guidance to the primary operator.

The Investigator will follow the procedure technique outlined in LM0001, PEPNS System Operator's Manual.

Prior to the start of electrical stimulation, the subject's diaphragm thickness may be measured using ultrasound and the subject will have a 12 lead ECG. In addition, baseline standard blood gasses such as pH and paO_2 , paCO_2 , SaO_2 , HCO_3 etc. and exhaled gas analysis such as end-tidal CO_2 data will be garnered for up to 24 hours prior to stimulation.

A four pole pacing lead electrodes will be percutaneously placed beside the phrenic nerves using ultrasound guidance and the ultrasound screen shots will be captured if possible. The ease of gain pacing lead access and setup will be assessed and logged.

The subjects phrenic nerve(s) will then be electrically stimulated for up to 48 hours and device and procedure information, ventilation and PEPNS System stimulation will be recorded. In addition, patient vital signs including heart and respiratory rate, blood pressure, temperature, pH, paCO_2 , paO_2 , hematocrit, end-tidal CO_2 , will be collected when available unless otherwise specified in table 1 below. If the patient is weaned from the mechanical ventilator during this time the time to weaning will also be recorded. Also, a chest x-ray will be obtained if the patient has not had one in the last 30 days. In addition, Critical Care Pain Observation Tool^{22,23} (CPOT) and Richmond Agitation & Sedation Scale^{24,25} (RASS) assessments will be administered prior to the electrical stimulation and every 6 hours during it. Patients will also be physically observed for any muscle twitching during the simulation period to try and determine if any other nerves were stimulated. Diaphragm thickness may be measured again at 24 and 48 hours or at the end of the stimulation period.

The ability of the pacing lead to accommodate neck movement and patient positional changes will also be assessed and logged during electrical stimulation.

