2. ANALYSIS OBJECTIVES

The company informed the FDA of plans to conduct a First in Human feasibility study within an OUS Tier I country (Canada, Europe or Australia) and stated:

As part of this study the following would be evaluated

- a) Confirmation of the stimulation leads are easily deployed under ultrasound guidance
- b) Confirmation that the diaphragm is easily stimulated without collateral stimulation similar to the Taira publication in references.
- c) Confirmation of appropriate candidates for a pivotal study. Trending demonstrating that time to extubation is decreased when compared to historical data in similar patient population.

The first two patients enrolled in the trial will be analyzed specifically for safety of the procedure in terms of nerve damage which could result from electrical stimulation or mechanical damage due to lead insertion, patient movement or lead removal and any other adverse events. Compound motor action potential and nerve conduction time between the neck and diaphragm will be evaluated in the first two pilot patients. Since these patients are stimulated on the left phrenic nerve only, they will be included for the safety analysis only. The enrollment of subsequent patients was contingent upon these patients showing no damage to the phrenic nerve at ~30 days post stimulation in terms of the CMAP study, follow up x-ray and any reported adverse events deemed relevant to the procedure.

Primary and secondary endpoints for the study will be evaluated statistically in terms of per protocol (PP) and intent-to-treat (ITT) analysis. The clinical study protocol CIP0001 defined intent-to-treat as "All patients that were attempted to be treated with the PEPNS System but the procedure was aborted." The

	PEPNS Study Statistical Analysis Plan <small>CONFIDENTIAL: THIS DOCUMENT AND ALL INFORMATION CONTAINED HEREIN IS PROPRIETARY TO STIMDIA MEDICAL, INC. AND IS NOT TO BE DISCLOSED WITHOUT THE EXPRESS WRITTEN PERMISSION OF STIMDIA MEDICAL, INC.</small>	Document Number SAP0001	Rev. Level 1
---	--	-----------------------------------	------------------------

primary analysis will be per protocol and the secondary analysis will be intent-to-treat. Time of weaning from mechanical ventilation and diaphragm thickness from 0 to 48 hours will also be analyzed.

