In addition, there may be additional analyses conducted and other tables and graphs created for the final clinical study report based on the outcomes of the initial analyses and additional data points of interest.

An interim analysis may be run and this was allowed in the protocol. See Statistical Methodology section for greater details.

PRIMARY ENDPOINTS

The primary endpoints for the study relate to the ability of the therapy to mobilize the diaphragm and of the PEPNS system to stimulate specific levels of work of breathing.

- Capture of the Left and/or Right Phrenic Nerve > 80% with an output parameter of < 10.5 volts.
- WOB (Work of Breathing) kept between 0.2 Joules/L and 2 Joules/L for 80% of stimulated breaths.

The capture of the left and right phrenic nerve will be demonstrated during setup and by maintaining the WOB between 0.2 and 2 Joules/L. The stimulation voltage resultant from the tissue impedance and the user set current will be logged and evaluated to ensure it is less than 10.5 volts. Capture will also be evaluated in terms of synchrony.

The ability of the stimulation pulse to capture the diaphragm will be assessed using WOB (Work of Breathing Measurements). A logistic regression model with successful capture as the outcome will be used. The model will include repeated measurements within a subject.

Model:

$\text{capture} = (\text{timepoint}) (\text{subject})$

where subject is a random effect, and the outcome of capture is yes/no based on whether the stimulation captures the diaphragm.

Capture for this analysis is defined as synchrony of the stimulated breath with the output parameter < 10.5 volts and WOB between 0.2 and 2.0 Joules/L. Synchrony will be achieved if the lag time between start of inspiration and start of stimulation is less than 88 ms.

Hypothesis:

H_0 : The proportion of capture is less than or equal to the performance goal (PG) of 80%. Note: This hypothesis used a 90% performance goal in the protocol for the purposes of sample size calculation to ensure that there would be sufficient data to achieve the 80% performance goal when taking into account lost to follow up due to death, etc.

$H_0: \hat{p}_1 \leq \text{PG}$

H_A : The proportion of capture is greater than the performance goal of 80%.

$H_A: \hat{p}_1 > \text{PG}$,

where \hat{p}_1 is the estimated proportion of capture from the logistic model accounting for repeated measurements within a subject.

Sample Size:

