ECG (electrocardiogram) will be reviewed before during and after electrical stimulation to ensure electrical stimulation is not adversely affecting the heart. This will be evaluated by an expert in the reading of ECGs.

	PEPNS Study Statistical Analysis Plan	Document Number SAP0001	Rev. Level 1
CONFIDENTIAL: THIS DOCUMENT AND ALL INFORMATION CONTAINED HEREIN IS PROPRIETARY TO STIMDIA MEDICAL, INC. AND IS NOT TO BE DISCLOSED WITHOUT THE EXPRESS WRITTEN PERMISSION OF STIMDIA MEDICAL, INC.			

Table 3: Patient Vitals and PEPNS Data

Patient ID	Age (yrs)	Weight (kg)	Height (cm)	Body Mass Index (BMI)	IV Line (Y/N)	ET / Trach (E/T)	Neck circumference at the cricoid cartilage (cm)	Screening Blood Pressure	PEPNS System Lead Preparation	PEPNS System Lead Placement	PEPNS System Lead Securement	Lead Removal/ Skin Closure Assessment	Twitching?	Follow-up X-Ray Normal?	Adverse Events?	Device Malfunctions?
P03S01																
P04S01																
P05S02																
P06S02																
P07S02																
P08S01																
P09S02																
P10S02																
P11S01																
P12S02																
Mean																
Stdev																

ADDITIONAL EVALUATIONS

Briefly state the overall scientific objectives of the analyses, including the key unanswered questions that these analyses are designed to address. If necessary, provide additional detail to formulate the objectives in statistical terms. Include a brief summary of how each objective will be addressed in the analyses.

The clinical effect of electrical stimulation will also be examined for the following:

- Time to weaning from mechanical ventilation data.
- Diaphragm thickness at 0, 24 and 48 hours.

The period of time each patient was on ventilation before electrical stimulation and the time to wean will be reported. The number of attempts to wean the patient before and after electrical stimulation will also be reported, if available.

The trend in diaphragm thickness increase/decrease for each patient and the aggregation of patients will be evaluated over time. The trend in diaphragm thickness based upon its initial thickness will also be evaluated. Correlations in diaphragm thickness increase and neck circumference will also be reviewed.

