3. ANALYSIS SETS/ POPULATIONS/SUBGROUPS

The only analysis populations that will be analyzed in this SAP are per protocol population as the primary analysis and intent-to-treat population as the secondary analysis. No other populations will be statistically analyzed since it is too small a data set to assess other subgroups.

There will be summary tables created for patient demographics. In general, summary statistics will include the mean, median, standard deviation, minimum and maximum for continuous measures and the number and frequency for categorical measures. This summary data will be reviewed to see if there are any trends that may have impacted study endpoints.

	PEPNS Study Statistical Analysis Plan <small>CONFIDENTIAL: THIS DOCUMENT AND ALL INFORMATION CONTAINED HEREIN IS PROPRIETARY TO STIMDIA MEDICAL, INC. AND IS NOT TO BE DISCLOSED WITHOUT THE EXPRESS WRITTEN PERMISSION OF STIMDIA MEDICAL, INC.</small>	Document Number SAP0001	Rev. Level 1
---	--	-----------------------------------	------------------------

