6. STATISTICAL METHODOLOGY

STATISTICAL PROCEDURES

The primary statistical methods used in this study will be descriptive where continuous variable will be summarized using means, medians, standard deviation, minimums and maximums and categorical variables will be summarized using frequencies and percent for each categorical level.

The primary endpoint will be analyzed using a logistic regression where diaphragm capture (yes/no) is the dependent variable and time point and subject are the independent fixed effect and random effect predictors. The point estimate of the diaphragm capture rate will be estimated from logistic regression model along with a two-sided 95% confidence interval. The lower bound of that confidence interval will be compared to the performance goal of 80%. If the lower bound is above 80%, then the endpoint will have been achieved.

Secondary endpoints will be summarized as noted in the secondary endpoints section. Each endpoint will be summarized descriptively.

Additional evaluations will also be summarized descriptively. In addition, diaphragm thickness over time will be modeled using regression analysis. The slope parameter and 95% confidence intervals will be presented. Additional diaphragm thickness analyses may be run.

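### Time to wean has no time origin and no rule for patients who die or stay ventilated, so the planned summary would cover only weaned patients and cannot support the benefit statements.

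*SAP*

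**What the plan says.** **Analysis.** SAP Section 2 (Additional Evaluations) states that "the time to wean will be reported", along with each patient's time on the ventilator before stimulation. SAP Section 6 adds: "Additional evaluations will also be summarized descriptively". SAP Section 3 sets the general format: "summary statistics will include the mean, median, standard deviation, minimum and maximum for continuous measures". Diaphragm thickness also gets a regression model; time to wean gets no method of its own. SAP Section 5, on missing values, does not mention weaning or death, and SAP Section 8 plans no statistical sensitivity analyses.

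**Collection.** For the stimulation period, Protocol Section 11.2 states: "If the patient is weaned from the mechanical ventilator during this time the time to weaning will also be recorded". Protocol Section 11.3 also collects weaning time at the 30-day visit.

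**Intended use.** SAP Section 2, item (c), lists: "Trending demonstrating that time to extubation is decreased when compared to historical data in similar patient population". Protocol Section 5, objective (a), is: "Determine whether pacing the diaphragm would be of benefit to the difficult to wean patient cohort in the ICU". Protocol Section 2 says the data will give evidence that stimulation improves time to weaning, and then that the trial is not powered to show a reduction. The design is single group, and no historical source, matching rule or method of comparison is named.

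**Death.** The SAP mentions "taking into account lost to follow up due to death, etc", but only to explain the 90% performance goal used in the capture sample size.

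**The concern.** A mean or median of weaning times can only be taken over patients who have one. A patient who dies on the ventilator, or is still on it at day 30, does not. With no censoring or competing-event rule, the analyst is left with the patients who weaned, and the worst outcomes disappear from the summary without being counted.

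These outcomes are foreseeable. Exclusion 2 removes only patients unlikely to survive 72 hours, while follow-up runs for 30 days.

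The result also carries weight. It is meant to be read against historical data as a decrease, and it bears on the benefit objective. In a single-arm study of 10 to 20 patients, an apparent shortening could come from who was counted rather than from the device. The missing time origin adds to this: intubation, start of stimulation and end of stimulation are all possible starting points, and a historical figure may use any of them.

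**Working it through.** The documents give no expected weaning time, death rate or sample size for this outcome, so there is no figure of the plan to reproduce. The following is an illustration, and every rate in it is an assumption.

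**Model.** Constant cause-specific hazards of weaning (w) and of death before weaning (d), total L = w + d, followed for 30 days (the Protocol's follow-up).

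**Inputs for the central case.** Underlying median time to wean 7 days; 20% die before weaning by day 30.

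1. w = ln 2 / 7 = 0.0990 per day.
2. d solves (d/L)(1 − e^(−30L)) = 0.20. This gives d = 0.0255 and L = 0.1245. Check: 0.0255/0.1245 × 0.976 = 0.200.
3. Weaned by day 30: 0.0990/0.1245 × 0.976 = 0.78. Still ventilated: e^(−30 × 0.1245) = 0.024.
4. Weaned-only median: −ln(1 − 0.5 × 0.976)/L = −ln(0.512)/0.1245 = 5.4 days.
5. Day by which half of **all** patients are weaned: −ln(1 − 0.5 L/w)/L = −ln(0.371)/0.1245 = 8.0 days.

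**Other assumed death risks, underlying median 7 days**

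| Die before weaning | Still ventilated at day 30 | Weaned-only median (days) | Half of all patients weaned by (day) |
|---|---|---|---|
| 0% | 5% | 6.5 | 7.0 |
| 10% | 4% | 6.0 | 7.4 |
| 20% | 2% | 5.4 | 8.0 |
| 30% | 1% | 4.8 | 8.9 |
| 40% | 1% | 4.1 | 11.0 |

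Over underlying medians of 4 to 10 days and death risks of 10% to 40%, the gap runs from about 0.6 days (3.6 against 4.2) to about 10.5 days (5.6 against 16.1). Under this model the weaned-only figure is always the shorter one.

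**How likely the problem is to arise.** The chance of at least one death among n patients is 1 − (1 − p)^n. For p = 10%, 20% and 30% it is 65%, 89% and 97% with 10 patients, and 88%, 99% and above 99% with 20.

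**Against a historical figure, with no device effect**

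- If the benchmark counts all patients and has the same hazards as the central case, the trial shows 5.4 against 8.0 days, an apparent shortening of about 2.6 days.
- If the benchmark is weaned-only with the same hazards, both give 5.4 days and there is no spurious gap.
- If the benchmark is weaned-only with 30% deaths, it gives 4.8 days and the trial looks about 0.6 days longer. With 10% deaths it gives 6.0 days and the trial looks about 0.6 days shorter.

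So understatement relative to all treated patients follows whenever patients without a weaning time are left out. The direction against history cannot be fixed until the benchmark is known.

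**The case against.** The strongest reply is that the SAP is silent rather than wrong. A reader might infer four things that the documents do not support.

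- **That the SAP decides to drop unweaned patients.** It sets no such restriction. The conditional recording in Protocol Section 11.2 covers only the stimulation period, and Section 11.3 collects weaning time again at day 30. The restriction is the practical result of a mean or median with no rule for missing times.
- **That the result is biased short against history.** This needs a benchmark that counts all patients, and none is named. For the same reason, one should not scale a 7.0-day mean by the share surviving (6.3, 5.6 or 4.9 days at 10%, 20% or 30% deaths). The 7.0 in that sum is a mean in a world without deaths, which no historical cohort supplies.
- **That the SAP forecasts deaths before weaning.** Its mention of death belongs to the capture sample size and gives no rate.
- **That a historical comparison is a worked-out analysis.** It appears only in the list of what the company told the FDA would be evaluated; the analysis sections contain none for weaning.

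It is also fair that weaning time is additional study data, not an endpoint, and that Protocol Section 2 disclaims power for it. That limits the consequence, but it addresses precision rather than selection, and the sentence before it still says the data will provide evidence. What remains is a summary that cannot be computed for every treated patient, attached to a claim that a single group cannot carry.

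**Conclusion.** The point holds in conditional form and should be corrected. As written, the weaning summary would in practice describe only patients who weaned and would understate the time to wean for all treated patients. In the central illustration this is about 5.4 against 8.0 days, a gap of 2.6 days. That size rests on constant hazards, a 7-day underlying median and 20% deaths before weaning, none of which comes from the documents. Whether the comparison with history would favour or disfavour the device is undetermined. In either case, an unpowered single-arm summary against an unnamed cohort cannot show a decrease or determine benefit.

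**What to change.** 1. Define the time origin for time to wean, and put the 30-day horizon on a stated clock.
2. For all treated patients, report the numbers weaned, dead before weaning and still ventilated at day 30.
3. Give the cumulative incidence of weaning with death as a competing event, with patients still ventilated censored at day 30, in place of the mean and median alone.
4. Either name a historical cohort with the same origin, event definition and handling of deaths, or reword SAP Section 2 item (c), Protocol Section 5 objective (a) and the evidence statement in Protocol Section 2 as descriptive, with no claim of a decreased time.

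The main inputs are already planned: weaning time at the 30-day visit (Protocol Section 11.3), deaths on the adverse event form (13.6.1) and exits on the disposition form (11.6.3). Ventilator-free days would be an alternative, but the 30-day visit does not list re-intubation, so that measure might need an added data item. The cost is a little more analysis, softer objective wording, and a weaning summary that may look less favourable.

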3. ANALYSIS SETS/ POPULATIONS/SUBGROUPS

The only analysis populations that will be analyzed in this SAP are per protocol population as the primary analysis and intent-to-treat population as the secondary analysis. No other populations will be statistically analyzed since it is too small a data set to assess other subgroups.

There will be summary tables created for patient demographics. In general, summary statistics will include the mean, median, standard deviation, minimum and maximum for continuous measures and the number and frequency for categorical measures. This summary data will be reviewed to see if there are any trends that may have impacted study endpoints.

	PEPNS Study Statistical Analysis Plan <small>CONFIDENTIAL: THIS DOCUMENT AND ALL INFORMATION CONTAINED HEREIN IS PROPRIETARY TO STIMDIA MEDICAL, INC. AND IS NOT TO BE DISCLOSED WITHOUT THE EXPRESS WRITTEN PERMISSION OF STIMDIA MEDICAL, INC.</small>	Document Number SAP0001	Rev. Level 1
---	--	-----------------------------------	------------------------

4. ENDPOINTS AND COVARIATES

There will be summary tables created for baseline and 30-day follow-up results. In general, summary statistics will include the mean, median, standard deviation, minimum and maximum for continuous measures and the number and frequency for categorical measures. This summary data will be reviewed to see if there are any trends that may have impacted study endpoints.

5. HANDLING OF MISSING VALUES AND OTHER DATA CONVENTIONS

The per protocol primary analysis will include all of the patients and all of the data garnered for them, as applicable. If there is sufficient data available, some additional analyses may be run that only includes patients that had no missing data or that were stimulated on both sides or that were stimulated only on one side to see if there was any impact on study results.

6. STATISTICAL METHODOLOGY

STATISTICAL PROCEDURES

The primary statistical methods used in this study will be descriptive where continuous variable will be summarized using means, medians, standard deviation, minimums and maximums and categorical variables will be summarized using frequencies and percent for each categorical level.

The primary endpoint will be analyzed using a logistic regression where diaphragm capture (yes/no) is the dependent variable and time point and subject are the independent fixed effect and random effect predictors. The point estimate of the diaphragm capture rate will be estimated from logistic regression model along with a two-sided 95% confidence interval. The lower bound of that confidence interval will be compared to the performance goal of 80%. If the lower bound is above 80%, then the endpoint will have been achieved.

Secondary endpoints will be summarized as noted in the secondary endpoints section. Each endpoint will be summarized descriptively.

Additional evaluations will also be summarized descriptively. In addition, diaphragm thickness over time will be modeled using regression analysis. The slope parameter and 95% confidence intervals will be presented. Additional diaphragm thickness analyses may be run.

If an interim analysis is performed, the database will be temporarily locked at the time of the interim analysis and the clinical study report will include the date that the data was transferred from the database to the statistician for the interim analysis. It will also specify whether or not the data had been monitored. The secondary end points and other remaining interim analyses will only be performed if the primary endpoints were met. If not, the study will continue to enroll patients and all study endpoints and additional analyses will be analyzed when enrollment has been completed. At the interim analysis the significance level used for testing will be 0.0125 which translates into calculating a 98.75% two-sided confidence interval on the capture rate and comparing the lower bound to 80%. At the final analysis (if needed) the significance level used for testing will be 0.0194 which translates into calculating a 98.06% two-sided confidence interval on the capture rate and comparing the lower bound to 80%. These levels were derived using a power cumulative error spending function with the parameter (rho) set to 1.0. This setting produces Pocock type boundaries (i.e. approximately equal spending for the two tests).

	PEPNS Study Statistical Analysis Plan <small>CONFIDENTIAL: THIS DOCUMENT AND ALL INFORMATION CONTAINED HEREIN IS PROPRIETARY TO STIMDIA MEDICAL, INC. AND IS NOT TO BE DISCLOSED WITHOUT THE EXPRESS WRITTEN PERMISSION OF STIMDIA MEDICAL, INC.</small>	Document Number SAP0001	Rev. Level 1
---	--	-----------------------------------	------------------------

7. MEASURES TO ADJUST FOR MULTIPLICITY, CONFOUNDERS, HETEROGENEITY, ETC.

Since the study cohort was 9 Caucasian men and 1 Caucasian woman and study was very small no heterogeneity, multiplicity or confounder statistical analyses will be run. However, summary data may be presented for the different types of patients (neuro trauma, COPD etc.) to try and see if there were any trends or if therapy was more effective for one of the patient populations since this was one of the study objectives.

To see if the type of patient may have impacted the primary endpoint of diaphragm capture, the primary analysis will be rerun with type of patient added into the logistic regression as an independent predictor. A confidence interval will be constructed about the coefficient for type of patient and if that confidence interval overlaps zero then it will be assumed that the type of patient did not impact the primary endpoint.

